2.6 Summary

The current study is a proof of concept study to determine whether an extended release film could deliver drug for seven days. Two film formulations which differ by dissolution and spreadability will be compared. It is appropriate to advance these two formulations of MK-2048 film into a clinical trial for safety given that the individual ingredients used in the film have a history of safe use in the vaginal compartment. The extended release platform may prove to be an effective drug delivery system with the potential to be used with many medications

3 OBJECTIVES

3.1 Primary Objectives:

- To assess the safety of a single dose of two formulations of an MK-2048 vaginal film which is intended for extended release of antiretroviral drugs.

3.2 Primary Endpoints:

- Grade 2 or higher Adverse Events

3.3 Secondary Objectives:

- Pharmacokinetics: To describe the pharmacokinetics of MK-2048 drug at 0, 3, 5, 7, 10, 14, and 28 days after film insertion
- Acceptability: To describe the acceptability of two formulations of the MK-2048 vaginal film and identify qualities associated with higher or lower degrees of acceptability

3.4 Secondary Endpoint:

- MK-2048 concentrations in plasma, tissue homogenate, CVL, and rectal and vaginal swab eluents, comparing the two film types
- Acceptability: Self-reported assessment of qualities of the experience with the films drawn from existing survey on microbicidal films, and general acceptability ratings drawn from market research methodology

3.5 Exploratory Objectives:

- To compare the effects of two formulations of the MK-2048 vaginal film on the vaginal microbiota and glycome pre and post study product use
- To describe the pharmacokinetics of Eudragit® polymer to ensure that polymer persistence is proportional to drug release.
- To describe the protective effect of MK-2048 film against HIV in an *ex vivo* biopsy challenge model using cervical tissue

3.6 Exploratory Endpoints:

- Vaginal Microenvironment
 - Quantitative vaginal cultures and quantitative PCR for selected microbiota from vaginal swab
 - Nugent score from vaginal swab
 - Levels of anti-viral activity in CVL
 - Levels of glycoproteins and mucins in CVL
 - Levels of biomarkers of innate immunity in CVL
- Eudragit® pharmacokinetics
 - Eudragit® levels in CVL
- Ex vivo challenge: HIV infection of cervical tissue as measured by HIV-1 p24 replication by ELISA and confirmed either by immunohistochemistry or quantitative PCR assessment of integrated provirus in HIV-1 exposed cervical biopsies

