Protocol Co-chair: [name]

Sample Size: Approximately 48

Study Population: HIV-uninfected women, 18 – 45 years old

Study Sites: UPMC Magee-Womens Hospital, Pittsburgh, PA

Study Design: A phase I, 2 arm, single site, randomized clinical trial

Visit 1	Visit 2	Visit 3	Visit 4	Visit 5	Visit 6	Visit 7	Visit 8
Screen	Enroll Day 0	Day 3	Day 5	Day 7	Day 10	Day 14	Day 28

Study Duration: Accrual of approximately 48 participants is expected to take 9 months. The expected duration of study participation for each participant will be approximately 5-10 weeks. This includes the screening period. After enrollment, the study duration is 4 weeks

Study Products: One dose MK-2048 vaginal film (2" x 2" size). Participants will be randomized to one of two formulations- high and low ammonio methacrylate copolymer type B (Eudragit®). Both films contain 30mg of MK-2048.

Study Regimen: All participants will be randomized to receive a single dose of a vaginal film containing MK-2048 (either the high Eudragit® or low Eudragit® formulation). The film will be inserted by a clinician on the day of enrollment. Vaginal swabs and plasma will be collected at days 0, 3, 5, 7, 10, 14 and 28 for all participants. On the day of enrollment, some participants may elect to participate in immediate post insertion sample collection (vaginal swab and plasma) at one or two time points within 6 hours of insertion. Genital biopsy samples and a rectal swab will be obtained on day 7, and cervicovaginal lavage will be collected at screening and days 14 and 28.

Primary Objectives:

- To assess the safety of a single dose of two formulations of an MK-2048 vaginal film which is intended for extended release of the antiretroviral drug

Endpoints:

- Grade 2 or higher Adverse Events

Secondary Objectives:

- To describe the pharmacokinetics of MK-2048 drug at 0, 3, 5, 7, 10, 14, and 28 days after film insertion
- To describe the acceptability of two formulations of the MK-2048 vaginal film and identify qualities associated with higher or lower degrees of acceptability

Secondary Endpoint:

- MK-2048 concentrations in plasma, cervical tissue homogenate, CVL, rectal and vaginal swab eluents
- Self-reported assessment of qualities of the experience with the films drawn from existing survey on microbicidal films, and general acceptability ratings drawn from market research methodology

Exploratory Objectives:

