7.4 Visit 3, 4, 5, 6, 7 and 8: Follow-Up Visits

Visit 3, 4, 5, 6, 7 and 8 procedures are outlined in Table 4. The windows around these study visits are as follows:

Visit 3: Day 3 (2-4)

Visit 4: Day 5 (5-6)

Visit 5: Day 7 (7-8)

Visit 6: Day 10 (9-12)

Visit 7: Day 14 (13-16)

Visit 8: Day 28 (24-32)

Two cervical biopsies will be obtained at Visit 5 only. A CVL will be performed at Visits 7 and 8. Residual drug, if present, will be removed during the CVL at Visit 7. The purpose of Visit 8 is to provide a final safety assessment.

Table 3: Follow-up Visit Procedures

VISIT 3, 4, 5, 6, 7, 8 FOLLOW-UP VISITS	
Component	Procedure/Analysis
ADMINISTRATIVE	
 • Collect/Update Contact Information • Visit Questionnaire • Update medical history and concomitant medications • Protocol counseling excluding Visit 8 (including effective birth control, sexual practices restrictions and vaginal product use) • Assess/Document Adverse Events • Schedule Next Study Visit (excluding Visit 8) • Participant Reimbursement
ACCEPTABILITY	
 • Acceptability Questionnaire (Visit 5 ONLY; prior to biopsy)
BLOOD	
 • MK-2048 level
URINE	
 • Pregnancy test (Visit 5 & 8 and as clinically indicated) • Urine dipstick, as clinically indicated
VAGINAL	
 • pH • Wet Mount, prn • Trichomonas (NAAT), as clinically indicated • Gram Stain • Quantitative Vaginal Culture • Quantitative PCR for microbiota • Vaginal swab for MK-2048 level • Vaginal sample for Future Use*
RECTAL	
 • Rectal swab for MK 2048 (Visit 5 ONLY)
CERVICAL	
 • GC/CT (NAAT), as clinically indicated • Cervical biopsies- two adequate (Visit 5 ONLY) • Cervical sample for Future Use*
CVL (Visits 7 and 8 only)	
 • Levels of antiviral activity • • Levels of glycoproteins and mucins • Levels of cytokines & innate immunity factors • MK-2048 level • Eudragit® levels
PHYSICAL EXAM	
 • Physical Exam, as clinically indicated • Vital Signs (BP)

PELVIC EXAM	
 • Bimanual Exam, as clinically indicated • External Genital & Speculum Exam
--------------------	--

* For participants who have consented to the collection of samples for future use and use of left-over samples for future studies.

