9.3.2 Secondary and Exploratory Endpoints

The secondary and exploratory endpoints of this study are as follows:

Secondary: MK-2048 pharmacokinetics

MK-2048 concentrations in plasma, tissue homogenate, and CVL rectal and vaginal swab eluents, comparing the two film formulations sampled at enrollment and post-enrollment time-points through Visit 8

Secondary: Acceptability

Reports of overall acceptability of the film and qualities of the experience with the film will be measured using a self-report survey drawing items from two sources. Overall acceptability is measured using standard language in market research methodology, each using a 5-point agreement scale followed by an open-ended explanation. Assessment of film-specific qualities of the experience is assessed by a 9-item scale drawn from previous research with participant-inserted films. Questions assess perceptions of leaking, vaginal dryness, and sensation of the film inside the vagina during and after insertion.

Exploratory: Vaginal Microenvironment

Given that there is no non-product use arm, participants will serve as their own control. Assessment of baseline microenvironment will take place during the Enrollment visit with the

exception of CVL properties. CVL will be obtained at the Screening visit so that the microenvironment can recover prior to study product administration at the enrollment visit.

Levels of lectin binding and mucins measured in CVL samples

Endogenous and exogenous glycolytic enzymes, formulated microbicide products, and microbial flora interact with mucins and may alter their structure and function. These alterations may be detected with lectins, which are sugar specific binding molecules, and can be bound to reporter molecules (such as horseradish peroxidase) in an ELISA type assay.

Nugent Score

Clinically significant changes in vaginal flora will be evaluated by a change in the Nugent score baseline (Visit 2, pre-exposure) through Visit 7. The Nugent score is graded 1 to 10 as follows:

Normal, 0 to 3

Intermediate, 4 to 6

BV, 7-10

Any shift from normal at baseline to intermediate or BV at Visit 3, 4, 5, 6, 7, or 8 or shift from intermediate or BV to normal at Visit 3, 4, 5, 6, 7, or 8 will be considered a scientifically meaningful change in vaginal microbiota.

Quantitative vaginal cultures and quantitative PCR

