9.7.3 Secondary and Exploratory Endpoint Analysis

Summary statistics of frequencies and percentages will be provided for categorical data. Means and standard deviations or medians and ranges will be provided for continuous data. Methods for the analyses of the secondary endpoints are described below.

Student's t- and Mann-Whitney U tests will be used, where appropriate, to evaluate differences in the following continuous variables between the study arms: MK-2048 concentrations in plasma, rectal and vaginal swab eluents, and genital tissue, levels of glycoproteins and mucins in CVL, levels of cytokines and innate immunity factors, and antiviral activity in CVL. Between group pre- to post-exposure changes in the above endpoints will also be evaluated using Student's t- and Mann-Whitney U tests, where appropriate, while paired Student's t- and Wilcoxon signed-rank tests will be used to evaluate these changes within each study arm. Mixed effects linear regression will be used to evaluate associations between days of exposure to study product and these outcomes.

Nugent score will be categorized as follows: normal (score 0-3), intermediate (score 4-6), and bacterial vaginosis (score 7-10). Differences in the categorized Nugent score pre and post exposure levels will be evaluated using Fisher's exact, while McNemar's tests will be used to evaluate pre- to post-exposure shifts between normal (score 0-3) and abnormal (score 4-10) vaginal microflora within each study arm. Generalized estimating equations will be used to evaluate differences in the marginal post exposure prevalence of bacterial vaginosis between the two film formulations.

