9.7.4 Analysis Cohort

The intent-to-treat cohort (ITT) will be defined as those who were randomized. It will be used for analyses of baseline characteristics, protocol deviations and violations, and trial conduct. The evaluable cohort (Eval) is a subset of ITT participants. Evaluable participants will be defined as participants who complete the Screening and Enrollment visits and return for their day 7 visit within the window for a safety assessment. Non-evaluable participants will be replaced.

TABLE 5: Statistical Analysis Plan

Endpoint	Variable	Statistics
Primary	Adverse Events	Frequency, Percent
	MK-2048 concentration	Mean, SD, Median, Range,
Secondary	Acceptability	Frequency, Percent

Exploratory	Persistence of Eudragit® in CVL defined as any concentration above the lower limit of quantification	Mean, SD, Median, Range
	Levels of glycoproteins and mucins, in CVL	Mean, SD, Median, Range
	Antiviral activity in CVL	Mean, SD, Median, Range
	Change in vaginal flora (Nugent score)	Frequency, Percent, Median, Range
	Culture/qPCR results from vaginal organisms - prevalence	Frequency, Percent
	Culture/qPCR results from vaginal organisms - concentration	Mean, SD, Median, Range
	Change in cytokine and innate immunity factors	Mean, SD, Median, Range
	HIV infection of cervical biopsies in ex vivo challenge	Mean, SD, Median, Range

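### The acceptability objective asks which film qualities go with acceptance, but the plan specifies no analysis that can show such an association

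*Combined protocol and SAP*

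**What the plan says.** The synopsis and section 3.3 both set the objective in two parts: "To describe the acceptability of two formulations of the MK-2048 vaginal film and identify qualities associated with higher or lower degrees of acceptability". The part at issue here is the second, to "identify qualities associated with higher or lower degrees of acceptability".

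Section 9.3.2 describes the measurements. Overall acceptability comes from market-research items, "each using a 5-point agreement scale followed by an open-ended explanation". For the film's qualities: "Assessment of film-specific qualities of the experience is assessed by a 9-item scale drawn from previous research with participant-inserted films".

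The questionnaire is given at Visit 2 after film insertion (7.3, Table 2) and again at day 7, before the biopsies (7.4, Table 3; Appendix 1).

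On analysis, section 9.7.3 states: "Methods for the analyses of the secondary endpoints are described below". The text that follows assigns t-tests, Mann-Whitney, signed-rank, Fisher and McNemar tests, mixed models and GEE to drug concentrations, CVL measures, Nugent score, microbiota and p24. Acceptability is not named. Its only analysis entry is the row in Table 5 (9.7.4): "Acceptability Frequency, Percent".

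**The concern.** The second part of the objective concerns a relation between two sets of variables: how women experienced the film and how acceptable they found it. The only planned output describes each variable alone. A team that followed the plan exactly could report what share of women noticed leaking and what share agreed that the film was acceptable. It could not report whether the women who noticed leaking were the ones who rated the film lower.

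There is also a prespecification issue. The plan does not name the items, the rating, the visit or the measure of association. Any association reported later would therefore rest on choices that could be made after the data were seen, with at least nine items to choose from. The primary safety endpoint, the sample size and the specimen schedule are not affected.

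**Working it through.** **1. Plan's own figures.** None is given for acceptability. The sample size (9.2) rests on exact binomial limits for Grade 2 or higher adverse events. Its headline figure reproduces: for 0/48, the upper limit is 1 − 0.025^(1/48) = 0.074, i.e. 7.4% as stated. It says nothing about acceptability.

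**2. Can frequencies and percents show an association?** Take a binary quality item and a binary rating in 48 women, with 24/48 reporting the quality and 24/48 rating the film acceptable. These joint tables (both / quality only / rating only / neither) have the same marginal percentages:

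| Joint table | Association |
|---|---|
| 24 / 0 / 0 / 24 | perfect positive |
| 12 / 12 / 12 / 12 | none |
| 0 / 24 / 24 / 0 | perfect negative |

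The planned summary would be 50% and 50% in all three. A cross-tabulation would separate them, but none is planned.

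**3. What could 48 women show?** The inputs are n = 48 in total and 24 per arm (9.2). The day-7 visit defines the evaluable cohort (9.7.4) and non-evaluable women are replaced, so n = 48 at Visit 5 is a reasonable planning value. The documents give no alpha or effect size for acceptability; two-sided 0.05 and correlations of 0.3 and 0.4 are assumed here for illustration.

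Fisher z for Spearman, SE = √(1.06/(n − 3)):

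- n = 48: SE = √(1.06/45) = 0.1535. The 95% half-width near zero is tanh(1.96 × 0.1535) = tanh(0.301) = 0.29.
- n = 24 (one arm): SE = √(1.06/21) = 0.2247. The half-width is tanh(0.440) = 0.41, which is why pooling over arms is preferable.

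Power ≈ Φ(atanh(ρ)/SE − z), n = 48:

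- ρ = 0.4, alpha 0.05: Φ(0.4236/0.1535 − 1.960) = Φ(0.80) = 0.79.
- ρ = 0.3, alpha 0.05: Φ(0.3095/0.1535 − 1.960) = Φ(0.06) = 0.52.
- ρ = 0.4, alpha 0.05/9: Φ(2.760 − 2.773) = Φ(−0.01) = 0.49.

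**4. Multiplicity.** For nine unadjusted tests at 0.05, if independent, the chance of at least one false positive is 1 − 0.95⁹ = 0.37. Items on one scale are likely to be correlated, so this is a guide and not an exact figure. With several overall ratings, the number of comparisons rises further.

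**The case against.** The strongest reply is that Table 5 was never meant to be exclusive. Every row lists summary statistics only. The adverse-event row shows frequency and percent although 9.7.2 adds Fisher's test, and the MK-2048 row shows means and medians although 9.7.3 adds tests and models. This is right. A reader might infer that the sponsor deliberately chose frequencies as the method for the association question, but the table does not support that. The defect is that 9.7.3, where the method should appear, omits acceptability.

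Second, each overall rating is followed by an open-ended explanation, which is a direct if qualitative way to learn why women liked or disliked the film. This also stands in part: the objective is not beyond reach, and the accurate statement is that it has no planned quantitative answer. No method for coding or summarising those explanations is given either.

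Third, this is a descriptive secondary objective in a small Phase I trial, and the analysis can be specified before the data are locked. That limits the importance of the point but does not remove the mismatch.

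Three stronger readings should be resisted:

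- *Percentages throw away the ordering of the 5-point scale.* They do not if all five categories are tabulated, and nothing in the plan collapses them.
- *A between-arm test of acceptability is missing.* The objective is to describe two formulations; section 3.4 attaches the comparison of film types to drug concentrations.
- *A test of change from Visit 2 to Visit 5 is missing.* No objective concerns change, and the documents do not say that the same items are asked at both visits.

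**Conclusion.** The point holds in a limited form. The association part of the acceptability objective has no specified quantitative analysis: 9.7.3 is silent on acceptability, and Table 5's entry is univariate. The data described in 9.3.2 would support an analysis, but only an exploratory one, with confidence intervals of roughly ±0.29 around a correlation near zero. The 79% power at a correlation of 0.4 should not be quoted alone, since it applies to one unadjusted test and falls to about 49% at 0.05/9.

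These figures assume 48 completed questionnaires at Visit 5, items that can be ranked, and two-sided 0.05. The documents state the 5-point format only for overall acceptability. They do not give the response format of the nine items or the number of overall ratings. The conclusion that marginal percentages cannot show association depends on none of these assumptions. The point is worth correcting, but it has no bearing on the safety conclusions.

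**What to change.** In 9.7.3 and the acceptability row of Table 5, add:

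- The time point: Visit 5, before biopsy.
- An association estimate with 95% CI between each of the nine quality items and the overall acceptability rating(s), pooled over arms and adjusted for or stratified by arm. Use Spearman correlation or a proportional-odds model if the items are ordinal, and otherwise a suitable rank or cross-tabulated measure. State the response format of the items.
- A statement that these results are descriptive because several items are examined.
- How the open-ended explanations will be coded and summarised next to the estimates.

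Alternatively, shorten the objective in the synopsis and section 3.3 to describing acceptability. Neither route needs new data, visits or participants. The first costs SAP wording and a little more analysis, and its estimates will be imprecise. The second costs only wording but gives up the question.

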4 STUDY DESIGN

4.1 Identification of Study Design

This is, single site, double blinded study.

4.2 Summary of Major Endpoints

Grade 2 or higher Adverse Events

4.3 Description of Study Population

The study population will be HIV-uninfected women who meet criteria outlined in Section 5.

4.4 Time to Complete Accrual

Accrual is expected to be completed in approximately 9 months.

4.5 Study Groups

All participants will be randomized to one of two MK-2048 films: a high Eudragit® film or a low Eudragit® film.

4.6 Expected Duration of Participation

The duration of study participation per woman is expected to be approximately 5-10 weeks. This includes the screening period.

4.7 Site

There is a single study site: UPMC Magee-Womens Hospital, Pittsburgh, PA.

5 STUDY POPULATION

5.1 Selection of the Study Population

The inclusion and exclusion criteria in this section will be utilized to ensure the appropriate selection of study participants.

5.2 Recruitment

Participants will be recruited from a variety of sources including the ambulatory clinic of Magee-Womens Hospital and the surrounding population. Participants will also be referred to the study from other local research projects and other health and social service providers serving the target study population. Recruitment strategies will be used that have been shown to be successful in several prior studies of topical microbicides. Recruitment materials will be approved by the University of Pittsburgh Institutional Review Board.

5.3 Retention

Once a participant is enrolled, the study site will make every effort to retain her in follow-up to minimize possible bias associated with loss-to-follow-up. The site will implement the following procedures to enhance retention:

- Thorough explanation of the study visit schedule and procedural requirements during the informed consent process and re-emphasis at each study visit.
- Thorough explanation of the importance of both groups to the overall success of the study.
- Collection of detailed locator information at the study screening visits, and active review and updating of this information at each subsequent visit.
- Use of appropriate and timely visit reminder mechanisms.

- Immediate follow-up on missed visits.

Study sites will use a participant tracking mechanism to facilitate visit scheduling and timely identification and follow-up on missed visits.

5.4 Inclusion Criteria

Women must meet all the following criteria to be eligible for inclusion in the study:

- 1) Age 18 through 45 years (inclusive) at screening
- 2) Able and willing to provide written informed consent.
- 3) Willing to use an effective method of birth control throughout the duration of the study. Examples of effective methods include: hormonal methods (other than NuvaRing®), IUD, bilateral tubal ligation, same sex partner, partner with a vasectomy, abstinence (defined as no vaginal sex for one month prior to screening).
- 4) Able and willing to provide adequate locator information
- 5) HIV-uninfected based on testing performed by study staff at screening (per algorithm in Appendix II)
- 6) In general good health as determined by the site clinician
- 7) Agree to be sexually abstinent, including use of sex toys, from V2 (Enrollment) until V7 (7 days after the biopsy visit) and 48 hours prior to all study visits.
- 8) Agree to refrain from use of vaginal device or products (for example, lubricants, creams, suppositories) throughout participation in the study. Tampons may be used except between V5 (biopsy visit) and V7 (day 14).
- 9) Willingness to undergo all study-related assessments and follow all study-related procedures
- 10) At screening and enrollment, agrees not to participate in other research studies involving drugs, medical devices, or vaginal products while enrolled in this trial
- 11) Participants over the age of 21 (inclusive) must have documentation of a satisfactory Pap within three years prior to Enrollment consistent with Grade 0 according to the Female Genital Grading Table for Use in Microbicide Studies Addendum 1 (Dated November 2007) to the DAIDS Table for Grading Adult and Pediatric Adverse Events, Corrected Version 2.1, July 2017, or satisfactory evaluation with no treatment required of grade 1 or higher Pap results. If no documentation of a Pap smear can be provided, a Pap smear will be collected at the screening visit.

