5.5 Exclusion Criteria

Women who meet any of the following criteria will be excluded from the study. Of note, the study is limited to premenopausal women with an intact uterus because the mucosal immune environment differs substantially between pre- and post- menopausal women. Therefore, inclusion of post-menopausal women would introduce heterogeneity into the population.

- 1.) Menopause (as defined as amenorrhea for one year or more without an alternative etiology)
- 2.) Hysterectomy
- 3.) Participant report of any of the following:
 - a) Known adverse reaction to any of the study products (ever)
 - b) Non- therapeutic injection drug use in the 12 months prior to Screening
 - c) Surgical procedure involving the pelvis in the 60 days prior to enrollment (includes dilation and curettage or evacuation, and cryosurgery; does not include cervical biopsy for evaluation of an abnormal pap smear)
 - d) Participation in a drug, spermicide and/or microbicide study in the 30 days prior to enrollment
 - e) Currently pregnant or pregnancy within 42 days prior to enrollment
 - f) Currently lactating
 - g) Use of a diaphragm, NuvaRing®, or spermicide for contraception
- 4.) Urogenital infection or suspected infection within 7 days of enrollment including: symptomatic candidiasis, trichomonas vaginalis, and symptomatic bacterial vaginosis; or cervical infection, including *N. gonorrhoeae* (GC), *C. trachomatis* (CT), or mucopurulent cervicitis; syphilis; HSV lesions, or other sores (Note: seropositive HSV without active lesions will not be excluded); acute pelvic inflammatory disease; urinary tract infection; recent exposure to a partner with GC, CT, Trichomonas, syphilis, or NGU
- 5.) Antibiotic or antifungal therapy (vaginal or systemic) within 7 days of enrollment
- 6.) As determined by the PI, has any significant uncontrolled active or chronic cardiovascular, renal, liver, hematologic, neurologic, gastrointestinal, psychiatric, endocrine *including poorly controlled diabetes), respiratory, immunologic disorder or infectious disease
- 7.) Menses-like bleeding at the time of the Enrollment visit* or expected menses-like bleeding within 14 days of the Enrollment visit
(*Women who have vaginal bleeding at the scheduled Enrollment visit may return at a different date to be re-examined and possibly enrolled provided they are still within the screening window and meet all criteria.)

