6.6 Concomitant Medications

Enrolled study participants may use concomitant medications during study participation. All concomitant medications, over-the-counter preparations, vitamins and nutritional supplements, recreational drugs, and herbal preparations will be recorded on the concomitant medications log form.

All participants will be counseled to avoid the use of spermicide and other non-study vaginal products (other than tampons during menstruation and female condoms) while participating in the study. Participants who report use of these products will be counseled regarding the use of alternative methods; however reported use of these products does not require any change in study product administration or follow-up procedures. Condoms, if provided by study staff, will not be coated with any type of spermicide.

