7.3 Visit 2: Enrollment

Subjects who meet the inclusion and exclusion criteria following the Screening visit may schedule an Enrollment visit. Care will be taken to schedule the Enrollment visit at a time when the participant is not expecting to be actively bleeding or anticipating her menses within 14 days.

Before performing any enrollment procedures, study staff will confirm eligibility. The participant will undergo a pelvic examination. Pelvic specimens as described below will be collected and the study staff will assess for bleeding. If no bleeding or other exclusionary findings are evident, the participant will then be randomized to study product. The act of randomization is considered the

act of enrollment for this study. Subjects with menses like vaginal bleeding at the Enrollment visit will not be randomized/enrolled at that time. These subjects may be rescheduled if vaginal bleeding resolves before 45 days from Screening have elapsed. If vaginal bleeding does not resolve during the window period, and the subject expresses interest in enrollment for the study, she may be rescreened.

After eligibility is confirmed, the site staff will go to the Pharmacy to obtain the study product. The clinician will insert a speculum and then place the film in the proximal third of the vagina under direct visualization per the SOP. After film placement, participants will be scheduled for Visit 3. Participants who agree to optional additional PK sampling will undergo blood draw and blind vaginal swab sampling for drug levels at 1-2 time points within the first 6 hours post insertion.

Table 2: Visit 2 Procedures

VISIT 2: ENROLLMENT – DAY 0 (Day 1 of Product Use)	
Component	Procedure/Analysis
ADMINISTRATIVE	
 • Review/Confirm Eligibility • Collect/Update Contact Information • Visit Questionnaire • Update medical history and concomitant medications • Screening Results • Protocol counseling (including effective birth control, sexual practices restrictions and vaginal product use) • Assess/Document Adverse Events • Schedule Next Study Visit • Participant Reimbursement
ACCEPTABILITY	
 • Acceptability Questionnaire (post film insertion)
BLOOD	
 • Baseline MK-2048 level • Optional MK-2048 level *
URINE	
 • Pregnancy test • Urine dipstick, as clinically indicated

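### Tampons are not restricted between film insertion and Day 7, and sections 5.4(8) and 6.6 disagree on when they are allowed: a minor point with a cheap fix

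*Combined protocol and SAP*

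**What the plan says.** - **Section 5.4, criterion 8.** Vaginal devices and products are to be avoided throughout participation, with one exception: "Tampons may be used except between V5 (biopsy visit) and V7 (day 14"). V5 is the Day 7 biopsy visit.
- **Section 5.4, criterion 7.** Over a wider span participants must "Agree to be sexually abstinent, including use of sex toys, from V2 (Enrollment) until V7 (7 days after the biopsy visit").
- **Section 6.6.** Participants are counseled to avoid non-study vaginal products, "other than tampons during menstruation and female condoms) while participating in the study". It adds that "reported use of these products does not require any change in study product administration or follow-up procedures".
- **Section 5.5, exclusion 7.** A woman is excluded for "expected menses-like bleeding within 14 days of the Enrollment visit". Section 7.3 schedules enrollment for when she is "not expecting to be actively bleeding or anticipating her menses within 14 days".
- **Section 11.1.2.** Vaginal sampling is to be gentle enough to leave the film undisturbed.
- **Section 2.6.** The study's purpose is to "determine whether an extended release film could deliver drug for seven days".
- **Sections 9.7.3 and 9.7.4 and Table 5.** MK-2048 concentrations are summarized by mean, SD, median and range, and compared between arms with t or Mann-Whitney tests. There is no rule for tampon use or film loss. To be evaluable, a woman must complete Screening and Enrollment and attend the Day 7 visit in window.

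**The concern.** The tampon restriction starts at the biopsy visit, so it covers the week after the biopsy but not the week after insertion. In that earlier week the film lies in the proximal third of the vagina. Swabs and plasma are due on Days 3, 5 and 7, and the only cervical tissue and rectal samples are taken at Day 7. One film is given and it is not replaced.

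Other parts of the protocol protect the film over these days, through abstinence (including sex toys) from V2 and through careful swabbing. Tampons are the gap. If one carried out film or drug, the low level that followed would be read as short delivery by the formulation, and the analysis plan has no step that would separate the two.

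**Working it through.** **1. The plan's own sizing figure.** The sample size rests only on exact binomial (Clopper-Pearson) intervals for Grade 2 or higher adverse events. Recomputed, 0/48 gives an upper bound of 7.4% and 0/24 gives 14.2%, as printed. All 13 rows of the n = 24 half of Table 4 reproduce. Of the n = 48 rows checked, 0, 4 and 24 events agree, and 5/48 gives 3.5 to 22.7% against 3.4 to 22.6% printed, a last-digit difference. None of these figures depends on film retention.

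**2. The two tampon rules side by side.**

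| Period | 5.4(8) | 6.6 (counseling) |
|---|---|---|
| V2 to V5 (Days 0 to 7) | permitted, no condition | exempt only during menstruation |
| V5 to V7 (Days 7 to 14) | barred | exempt during menstruation |
| V7 to V8 (Days 14 to 28) | permitted, no condition | exempt only during menstruation |

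The sections differ in every row. Section 6.6 is narrower in the first and third periods and looser in the second.

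**3. How much early use to expect.** Exclusion 7 and section 7.3 remove expected menses to Day 14. Read with 6.6, use within the counseling before Day 7 is limited to unexpected bleeding. The documents give no rate for this.

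**4. Illustration of size.**
- Baseline: film visible in 56% at Day 7 in FAME-101 (section 2.2). That was the high-Eudragit placebo film. No clinical retention figure is given for the low-Eudragit film.
- t = share of women using a tampon on Days 0 to 7 (assumed).
- q = chance that a film still present is lost, given use (assumed).
- Film presence = 0.56 × (1 − t × q), so the drop is 0.56 × t × q, and the number of women is 48 times that.

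| t | q | Drop (points) | Women of 48 |
|---|---|---|---|
| 2% | 25% | 0.3 | 0.1 |
| 2% | 100% | 1.1 | 0.5 |
| 5% | 100% | 2.8 | 1.3 |
| 10% | 25% | 1.4 | 0.7 |
| 10% | 100% | 5.6 | 2.7 |
| 25% | 100% | 14.0 | 6.7 |

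For example, with t = 5% and q = 100%: 0.56 × 0.05 = 0.028, and 48 × 0.028 = 1.3. If use is confined to unexpected bleeding (taken as 2 to 5%), the drop is at most about 3 points. The last three rows need more use than sections 5.5, 6.6 and 7.3 together would suggest.

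**5. Chance of at least one user.** 1 − (1 − t)^48 gives 1 − 0.98^48 = 0.62 at t = 2% and 1 − 0.95^48 = 0.91 at t = 5%. Even rare use would probably occur in someone, so a handling rule is worth having.

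**The case against.** The case against acting is strong on size.

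- **Largely handled already.** The menses exclusion, the scheduling rule and the limit in 6.6 leave only unexpected bleeding, and counseling on vaginal products is repeated at every visit before V8. This stands, and is why the point is minor. It does not remove the conflict between 5.4(8) and 6.6.
- **The mechanism is inferred.** No passage shows that a tampon removes film or drug. In macaques the film stayed in place through menstruation and coitus (section 2.5). This stands, although withdrawing an absorbent product was not tested.
- **The same rule applies to both randomized, blinded arms.** This stands. A reader might infer a biased comparison between the films. That would need the two formulations to dislodge at different rates. They differ in dissolution and spreadability, so this is possible, but the documents do not show it.
- **Recording may already exist.** A visit questionnaire and a speculum exam occur at every follow-up visit. The questionnaire's content is not in the documents, so it cannot be said that tampon use goes unrecorded. What is missing is any rule in section 9.7 for using the information.
- **Leaving out samples after tampon use selects on a post-randomization event.** That event is linked to bleeding, which may itself alter vaginal concentrations. This stands, and it limits the re-analysis to a sensitivity summary.

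A reader might also multiply up single participants: one woman is 1/24 = 4.2 points of an arm and two are 8.3. Those figures would apply to a proportion with drug present at Day 7, which the plan does not define, and they hold for any participant affected by any cause. They do not measure the effect of tampons.

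**Conclusion.** The gap and the inconsistency are real. Criterion 5.4(8) leaves tampons permitted from insertion to Day 7, and 6.6 states a different rule for the same product. The consequence is small: slightly lower or noisier MK-2048 levels in both arms, at most about 3 points of Day 7 film presence if 2 to 5% of women use a tampon and every such use removes a film still present. Both rates are assumptions, and 56% comes from a placebo version of one formulation.

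It might be inferred that the seven-day proof of concept is in jeopardy. The documents do not support that, because expected exposure is rare and film removal is not demonstrated. The primary safety endpoint, the sample size of 48 and Table 4 are unaffected. This is a cheap improvement of minor severity.

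**What to change.** 1. Reconcile 5.4(8) and 6.6 so that the existing tampon restriction starts at film insertion and runs from V2 to V7, with the same wording in both places.
2. Confirm that the visit questionnaire records any tampon use, with its date, at Visits 3 to 7. Add one item if it does not.
3. In section 9.7.3, keep the all-samples summary of MK-2048 concentrations as the main result, and add a sensitivity summary without samples taken after reported tampon use.

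The cost is one phrase in each of two sections, possibly one questionnaire item, and one extra table. Visits, samples and sample size do not change. The downside is that women with unexpected spotting in the first week must use other protection. Because no menses are expected then, few should be affected.
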